11.1.7 Duration of Response

Duration of overall response: The duration of overall response is measured from the time measurement criteria are met for CR or PR (whichever is first recorded) until the first date that recurrent or progressive disease is objectively documented (taking as reference for progressive disease the smallest measurements recorded since the treatment started, or death due to any cause. Participants without events reported are censored at the last disease evaluation).

Duration of overall complete response: The duration of overall CR is measured from the time measurement criteria are first met for CR until the first date that progressive disease is objectively documented, or death due to any cause. Participants without events reported are censored at the last disease evaluation.

Duration of stable disease: Stable disease is measured from the start of the treatment until the criteria for progression are met, taking as reference the smallest measurements recorded since the treatment started, including the baseline measurements.

11.1.8 Response Review

The study will use the DF/HCC Tumor Imaging Metrics Core (TIMC) for central protocol measurements.

12. DATA REPORTING / REGULATORY REQUIREMENTS

Adverse event lists, guidelines, and instructions for AE reporting can be found in Section 7.0.

12.1 Data Reporting

12.1.1 Method

The Office of Data Quality (ODQ) will collect, manage, and perform quality checks on the data for this study.

12.1.2 Responsibility for Data Submission

Investigative sites within DF/HCC or DF/PCC are responsible for submitting data and/or data forms to the Office of Data Quality in accordance with DF/HCC SOPs.

12.2 Data Safety Monitoring

The DF/HCC Data and Safety Monitoring Committee (DSMC) will review and monitor toxicity and accrual data from this study. The committee is composed of clinical specialists with experience in oncology and who have no direct relationship with the study. Information that raises any questions about participant safety will be addressed with the overall PI and study team.

The DSMC will review each protocol up to four times a year or more often if required to review toxicity and accrual data. Information to be provided to the committee may include: up-to-date participant accrual; current dose level information; DLT information; all grade 2 or higher unexpected adverse events that have been reported; summary of all deaths occurring with 30 days of intervention for Phase I or II protocols; for gene therapy protocols, summary of all deaths while being treated and during active follow-up; any response information; audit results, and a summary provided by the study team. Other information (e.g. scans, laboratory values) will be provided upon request.

12.3 Collaborative Research and Future Use of Data and Specimens

Tissue, blood, bodily fluids, and other materials derived from these will be collected in this study to analyze genes, DNA, RNA, proteins and cells for the study's correlative endpoints and potential future research, utilizing new types of biomarker testing as it becomes available.

These samples and any data generated as a part of these clinical trials may be used for future research studies and may be provided to collaborating investigators both within and outside of the DF/HCC for either correlative endpoints or secondary use. Samples and data may be shared with outside non-profit academic investigators, as well as with for-profit pharmaceutical investigators or commercial entities, with whom we collaborate. When samples or data are sent to collaborators and when any research is performed on them, all information will be identified with a code, and will not contain any PHI, such as name, birthday, or MRNs.

In order to allow the greatest amount of research to be performed on the specimens and information generated as a part of this trial, researchers in this study may share results of genetic sequencing with other scientists. De-identified specimen or genetic data may be placed into one

of more publicly-accessible scientific databases, such as the National Institutes of Health's Database for Genotypes and Phenotypes (dbGaP). The results from the correlative research on this study will be shared with these public databases. Through such databases, researchers from around the world will have access to de-identified samples or data for future research. More detailed information, beyond the public database, may only be accessed by scientists at other research centers who have received special permission to review de-identified data

13. STATISTICAL CONSIDERATIONS

13.1 Study Design/Endpoints

This is a single-arm, two-stage phase 2 study to evaluate the response to abemaciclib monotherapy in patients with Rb-positive, triple negative metastatic breast cancer.

13.1.1 Primary objective and endpoint

To evaluate the efficacy of abemaciclib, as defined by objective response rate (ORR) in patients with Rb-positive triple-negative metastatic breast cancer (ORR as confirmed Complete Response (CR) or Partial Response (PR) per Response Evaluation Criteria in Solid Tumors (RECIST) Version 1.1).

13.1.2 Secondary efficacy endpoints

- 1) Progression-Free Survival (PFS)
- 2) Overall Survival (OS).
- 3) Disease control rate (DCR)
- 4) Clinical benefit rate (CBR)

13.2 Sample Size, Accrual Rate and Study Duration

This is a single-arm, two-stage phase 2 study in order to determine the efficacy of abemaciclib monotherapy in patients with metastatic RB-positive TNBC. There is no data for response to abemaciclib in patients with TNBC who are RB-positive. A response rate of 20% would be of clinical interest. A true response rate of 5% would not be of clinical interest. We have used a Simon optimal two-stage model with a one-sided type I error of 10% and type II error of 0.1 (90% power) to detect the difference between null (5%) and alternative (20%) objective response rates. The first stage of the study includes 12 patients with metastatic triple-negative breast cancer which is RB-positive. As of June 2018, it was discovered that a participant without measurable disease was registered and treated on this trial. As such, this participant is considered unevaluable in relation to the primary endpoint. Therefore, we plan to enroll a total of 13 participants to the first stage, with the expectation that 12 will be evaluable for response. The statistical plan will otherwise remain unchanged. If in the first stage there is at least one

response, accrual will continue to the second stage where an additional 25 patients will be enrolled. If there are at least 4 responses among the 37 evaluable patients, the regimen would be considered to be of clinical benefit worthy of further study (exact $\alpha=0.09$). If the true the response rate is 5%, the probability that the study would discontinue after stage I is 54%. The total accrual to the study will be 38 given the additional patient added for evaluation in the first stage.

13.3 Analysis of Primary Endpoints

Best overall response will be assessed among patients who received at least one dose of protocol therapy using RECIST 1.1 criteria. The objective response rate (CR+PR) will be reported with 95% confidence interval adjusting for two-stage design.

13.4 Analysis of Secondary Endpoints

Overall Survival: Overall Survival (OS) is defined as the time from randomization (or registration) to death due to any cause, or censored at date last known alive.

Progression-Free Survival: Progression-Free Survival (PFS) is defined as the time from randomization (or registration) to the earlier of progression (per RECIST 1.1) or death due to any cause. Participants alive without disease progression are censored at date of last disease evaluation.

PFS and OS will be described using the methods of Kaplan-Meier, and they will be presented with 95% confidence intervals.

Disease control rate: Disease control is defined as CR, PR, or SD \geq 16weeks per RECIST 1.1. Disease control rate will be reported with a 95% exact confidence interval.

Clinical benefit rate: is defined as CR, PR, or SD \geq 24weeks per RECIST 1.1. Clinical benefit rate will be reported with a 95% exact confidence interval.

Phospho-Rb reduction will be evaluated as a dichotomous endpoint from paired tumor assessment. It is anticipated that 60-70% of patients will have reduction in phospho-Rb after one cycle of protocol treatment. Due to the low anticipated response rate, disease control will be used as the primary evaluation of the marker in order to maintain power to detect an association with phospho-Rb reduction. Based on data from the Monarch-1 study in ER+ breast cancer (Dickler et al, ASCO 2016) a 34% disease control rate in the total study population would be anticipated if abemaciclib monotherapy is observed to have activity (lower than that observed in ER+ disease).

Assuming that 33 pairs of biopsies were evaluable for phospho-Rb (10% failure rate), we will have more than 85% power to detect a difference in the disease control rate if the rates are 53.3% among patients with phospho-Rb reduction and 5% among patients without phospho-Rb reduction. The following table gives the power of detecting the difference in disease control among patients with and without phospho-Rb reduction,

assuming the overall rate is 34% and with incidences of 60% and 70% phospho-Rb reduction

# of paired biopsies evaluable for phospho-Rb	Expected tumor with phospho-Rb reduction	DCR among pts with phospho-Rb reduction	DCR among pts without phospho-Rb reduction	Power
29	60%	53.3%	5%	81%
		50%	10%	56%
	70%	47.7%	2%	73%
		46.4%	5%	58%
33	60%	53.3%	5%	85%
		50%	10%	63%
	70%	47.7%	2%	76%
		46.4%	5%	60%

Phospho-Rb reduction will be evaluated using Fisher Exact test with two-sided alpha = 0.05. Exploratory analyses will additionally consider the other efficacy endpoints and quantitative measures of phospho-Rb reduction using logistic regression models. With a 20% probability of objective response overall, there will be 89% power to detect an improvement to 50% probability of response with a 1 standardized-unit increase in phosph-RB reduction (OR = 4.0). Power calculations were performed in East v6.3 (Cytel Inc.).

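### Optional efficiency gain: Fisher's exact test for phospho-Rb is valid, but its true size is about 3%; Boschloo's test would add about 3 to 11 power points from the same biopsies

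*Combined protocol and SAP*

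**What the plan says.** Section 1.3 lists, as a secondary objective, a comparison of clinical outcomes by phospho-Rb reduction. Section 13.4 makes reduction a yes/no variable from paired biopsies and takes disease control as the outcome: "disease control will be used as the primary evaluation of the marker in order to maintain power". The test is fixed in one sentence: "Phospho-Rb reduction will be evaluated using Fisher Exact test with two-sided alpha = 0.05".

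The design assumptions are also in Section 13.4:
- Sample: "Assuming that 33 pairs of biopsies were evaluable for phospho-Rb (10% failure rate"). The table also covers 29 pairs.
- Split: "It is anticipated that 60-70% of patients will have reduction in phospho-Rb after one cycle of protocol treatment".
- Table basis: "assuming the overall rate is 34% and with incidences of 60% and 70% phospho-Rb reduction".
- Main scenario: "53.3% among patients with phospho-Rb reduction and 5% among patients without phospho-Rb reduction", for which "we will have more than 85% power to detect a difference in the disease control rate".

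The stated powers are 81, 56, 73 and 58% for 29 pairs, and 85, 63, 76 and 60% for 33 pairs. The section does not give the true size of the test, mention an unconditional alternative, or give a reason for the conditional test.

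**The concern.** Fisher's test conditions on both margins of the 2x2 table. In small samples few p-values are then attainable, and the true error rate can sit well below the nominal level. In this single-arm study the design fixes neither the number of patients with marker reduction nor the number with disease control.

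The plan chose its outcome to protect power, yet six of its eight tabulated powers are below 80%. More pairs are hard to obtain. Biopsies are limited to accessible disease, can be waived, and need not be repeated if tissue is inadequate (Sections 3.1.17 and 9.7.1.1). A test that uses more of the 5% would raise power without another biopsy.

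**Working it through.** **Inputs (Section 13.4).** Two-sided alpha 0.05; 29 or 33 pairs (37 x 0.9 = 33.3); 60% or 70% with reduction; the four pairs of disease control rates in the table; common rate 34%. Rounded group sizes (reduction/no reduction):
- 0.6 x 29 = 17.4, giving 17/12
- 0.7 x 29 = 20.3, giving 20/9
- 0.6 x 33 = 19.8, giving 20/13
- 0.7 x 33 = 23.1, giving 23/10

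**Formulas.** For x of n1 and y of n2 with disease control, Fisher's two-sided p sums the hypergeometric probabilities of all tables no more probable than the observed one.
- Power = sum over all (x, y) of Bin(x; n1, p1) x Bin(y; n2, p2) x 1{reject}.
- Size at common rate r = the same sum with p1 = p2 = r; maximum size is taken over a fine grid of r.
- One-sided Boschloo p = the maximum over r of the probability that the one-sided Fisher p is as small as the one observed.

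Two two-sided versions were run. Version A orders tables by Fisher's two-sided p and takes the largest rejection region whose maximum size is at most 5%. Version B doubles the smaller one-sided Boschloo p.

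**Step 1: the plan's figures reproduce.** All eight stated powers are within 1 point of the exact Fisher power, so the table is right for Fisher's test.

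**Step 2: true size.**

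| Split | Fisher at 34% | Fisher max | A max | B max |
|---|---|---|---|---|
| 17/12 | 3.11% | 3.12% | 4.7% | 4.1% |
| 20/9 | 3.10% | 3.34% | 4.9% | 4.4% |
| 20/13 | 2.97% | 3.22% | 4.8% | 4.6% |
| 23/10 | 3.15% | 3.15% | 4.6% | 4.6% |

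Fisher's test leaves at least 5 - 3.3 = 1.7 points of alpha unused.

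**Step 3: power (%), with gain over exact Fisher.**

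| Split | Rates (%) | Stated | Fisher | A | B |
|---|---|---|---|---|---|
| 17/12 | 53.3 v 5 | 81 | 80.9 | 86.3 (+5.4) | 84.4 (+3.5) |
| 17/12 | 50 v 10 | 56 | 56.5 | 66.3 (+9.8) | 62.1 (+5.6) |
| 20/9 | 47.7 v 2 | 73 | 73.4 | 81.5 (+8.0) | 81.5 (+8.0) |
| 20/9 | 46.4 v 5 | 58 | 58.5 | 65.6 (+7.1) | 65.6 (+7.1) |
| 20/13 | 53.3 v 5 | 85 | 85.4 | 91.4 (+6.0) | 89.9 (+4.5) |
| 20/13 | 50 v 10 | 63 | 63.0 | 72.7 (+9.7) | 69.5 (+6.6) |
| 23/10 | 47.7 v 2 | 76 | 76.3 | 79.2 (+2.9) | 85.6 (+9.3) |
| 23/10 | 46.4 v 5 | 60 | 60.8 | 66.5 (+5.6) | 71.9 (+11.1) |

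Gains are taken from unrounded powers.

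**Step 4: where the gain comes from.** Version A contains the Fisher region by construction. Enumeration shows that version B also contains it at these four splits. An example of an added table is 6/20 v 0/13. With 6 controlled patients in all, the hypergeometric probabilities are C(20,6)/C(33,6) = 38,760/1,107,568 = 0.0350 for the observed table, and 25,740/1,107,568 = 0.0232 and 1,716/1,107,568 = 0.0015 for the less probable tables in the other tail. Fisher's p is 0.0350 + 0.0232 + 0.0015 = 0.060, which is not significant. Both Boschloo versions reject.

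**Step 5: sensitivity (version A).** Rounding the split the other way gives gains of 2.5 to 10.2 points. Averaging over a binomial split gives about 4.5 to 12.8. The maximum size stayed at or below 5% throughout.

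**The case against.** The plan makes no error here. Fisher's test controls the 5% level, its power table is correct, and the test, sidedness and alpha are all pre-specified. Fisher's test is conventional, its validity needs no maximisation over an unknown rate, and some statisticians prefer conditional inference on principle. All of that stands, and it is why this is an improvement and not a correction.

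The stakes are also limited. The comparison is secondary and drives no stopping or go/no-go rule; those rest on response rate (Section 13.2). A reader might infer that the biopsies are wasted under Fisher's test. The documents do not support that: Section 9.7.1.6 uses the same tissue for sequencing, expression and staining, and Section 13.4 adds exploratory logistic models of quantitative phospho-Rb change.

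The most useful objection is that naming Boschloo's test alone does not define the analysis. Versions A and B differ by up to about 6 points in a row (23/10, 47.7 v 2%: 79% v 86%). A replacement that left this open would be less fully pre-specified than the present sentence, so the fix must state the definition.

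**Conclusion.** The point holds as a low-cost efficiency gain. At the plan's splits Fisher's test has a true two-sided size of at most 3.1% to 3.3%. Boschloo's test stays at or below 5% (not exactly 5%), loses no Fisher rejection, and gains in all eight scenarios: 2.9 to 9.8 points under version A, 3.5 to 11.1 under version B.

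Two stronger readings are tempting and unsupported. One is that the test is invalid or the power table wrong; both are sound. The other is that the change would make the comparison well powered throughout. Below 80% there would still be five of eight rows under version A and four of eight under version B, against six now. The main scenario already has the 85% that the plan claims.

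The row figures assume the plan's disease control rates, independent binomial outcomes in the two groups, and fixed rounded splits. The direction of the result held in every variant tried.

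**What to change.** Replace the test sentence in Section 13.4 with:

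> Disease control will be compared by phospho-Rb reduction status (yes v no) using Boschloo's exact unconditional test, conditioning on the observed group sizes, with the two-sided p-value defined as twice the smaller one-sided Boschloo p-value, two-sided alpha 0.05. Fisher's exact p-value will also be shown.

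Make the change before the marker data are examined, so that the choice of test cannot depend on the result. Recompute the power table under the same definition. In table order it would read about 84, 62, 81 and 66% for 29 pairs, and about 90, 70, 86 and 72% for 33 pairs.

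The cost is one sentence and one recalculated table, using available statistical software, with no added patients or biopsies. The downside is that the test is less familiar and the inference is unconditional. Showing Fisher's p-value alongside serves readers who prefer the conditional test.

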A portion of the baseline biopsy will have RNA extracted. This RNA will then be subjected to analysis of gene expression by Affymetrix microarray and/or using the Nanostring nCounter platform. Tumors will be classified according to published algorithms to determine their individual TNBC subtype. We expect that the majority (but not all) of the RB-positive tumors will fall into the “Luminal Androgen Receptor” or “Mesenchymal Stem Like” subtypes, and as an exploratory analysis will determine if tumors within this subtype have a higher rate of response to abemaciclib. Additionally, in patients who consent, RNA extracted will be used to quantify the expression of several genes, including (but not limited to) those used to classify tumors into PAM50 subtypes[18], those identifying specific TNBC subtypes [19][8], and those that contribute to a signature of RB proficiency or deficiency. This will allow us to depict the landscape of gene expression for all tumors in this study, and also to determine in an exploratory fashion the correlation (or lack thereof) between RB positivity by IHC and “Rb-proficiency” by gene expression. The Nanostring assay will be performed at the BWH Center for Advanced Molecular Diagnostis (CAMD). Some portion of de-identified patient clinical information will be shared with Nanostring Technologies, with patient permission, in exchange for the kits needed to perform this assay.

Analysis of paired baseline and C2D1 biopsies

- a) Phospho-RB: FFPE tissue from baseline and C2D1 biopsies will be stained for p-RB (ser780) using protocols established at the Brigham and Women’s Hospital. Sections will be scored manually and the percentage of positive tumor cells will be recorded – a minimum of 200 cells will be counted. A tumor H score will be calculated. We will determine whether (i) baseline RB phosphorylation level predicts response to abemaciclib and (ii) whether suppression of RB phosphorylation after commencement of therapy is associated with an increased response rate.

- b) FFPE tissue from baseline and C2D1 biopsies will be stained for proteins involved in the regulation of cell proliferation in the lab of [name], PhD at Dana-Farber Cancer Institute.

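### Phospho-Rb reduction is related to outcome without baseline phospho-Rb in the model; if baseline is prognostic and correlated with reduction, the association could be mistaken for an effect of suppression (low priority)

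*Combined protocol and SAP*

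**What the plan says.** Section 13.4 codes phospho-Rb reduction as yes or no from the paired biopsies and makes disease control the main outcome for the marker. The test is fixed: "Phospho-Rb reduction will be evaluated using Fisher Exact test with two-sided alpha = 0.05". Beyond that, "Exploratory analyses will additionally consider the other efficacy endpoints". The same sentence goes on to name "quantitative measures of phospho-Rb reduction using logistic regression models". The power statement for the logistic model starts from this assumption: "With a 20% probability of objective response overall". It then says "there will be 89% power to detect an improvement to 50% probability of response" per standardized unit of reduction, an odds ratio of 4.0. Reduction is the only predictor mentioned, and no covariate list is given.

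Section 9.7.1.6 sets two questions for the paired biopsies. Question (i) is whether "baseline RB phosphorylation level predicts response to abemaciclib". Question (ii) turns to the change under treatment and asks if "suppression of RB phosphorylation after commencement of therapy is associated with an increased response rate". Percentage of positive cells and an H score are recorded at both time points. Nothing in either section puts baseline and reduction in the same model, and nothing says whether quantitative reduction is an absolute, percent or log-ratio change.

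**The concern.** If reduction is measured as an absolute change (baseline minus Cycle 2 Day 1), it contains the baseline value: a tumor with little phospho-Rb at baseline has little room to fall. If question (i) turns out to be true, an analysis of question (ii) that leaves baseline out mixes the two. The trial could then report an association that reflects starting level rather than suppression, or miss a real association if baseline acts in the opposite direction. Separating these is a main reason for taking a second biopsy. Two separate analyses, one for baseline and one for reduction, cannot show whether suppression matters at a given baseline.

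**Working it through.** **1. Reproduce the stated 89%.** Inputs from Section 13.4: overall response p = 0.20; odds ratio (0.50/0.50)/(0.20/0.80) = 4.0. The sample size and alpha of the logistic model are not stated; 33 pairs and two-sided 0.05 are taken from the Fisher test description. One-predictor formula for a normal covariate:

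power = Φ(√(n·p·(1−p))·ln OR − 1.96)
= Φ(√(33 × 0.16) × 1.386 − 1.96) = Φ(3.185 − 1.96) = Φ(1.225) = 0.890.

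This matches the plan. Other settings do not: n = 29 gives 0.848, n = 37 gives 0.921, n = 38 gives 0.928 (all two-sided), and n = 33 one-sided gives 0.938. So the model appears to have been powered with reduction as the sole predictor.

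**2. How closely absolute change is tied to baseline.** Let rho be the correlation between the baseline and Cycle 2 Day 1 values, with equal variances. Then corr(reduction, baseline) = √((1−rho)/2): 0.71 at rho = 0, 0.50 at rho = 0.5, 0.39 at rho = 0.7. It is positive for any rho below 1. The documents give no rho.

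**3. False-positive rates for disease control.** Simulation with 33 pairs, 34% disease control (Section 13.4), absolute change, and no effect of suppression given baseline. For the Fisher test, 65% of tumors are classed as reduced, the middle of the plan's 60-70%. Baseline odds ratio per SD and rho are assumptions.

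| Baseline OR per SD | Unadjusted logistic | Fisher |
|---|---|---|
| 1 (not prognostic) | about 6-7% | about 3% |
| 1.5 | about 8% at rho 0.7 | 3-5% over rho 0-0.8 |
| 2 | 15-25% for rho 0.5 down to 0; 10-12% at rho 0.7-0.8 | 6-10% for rho 0.5 down to 0 (5.1% at rho 0.5 in a second run); 4.3% at rho 0.7 |
| 3 | 24-44% for rho 0.5 down to 0; about 16% at rho 0.7 | 9.3% at rho 0.5; 7.1% at rho 0.7; about 17% at rho 0 |
| 3, reduction unrelated to baseline | 6.4% | 2.9% |

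With baseline added, the logistic test rejects in about 5-7%. The last row and the first row show that both conditions are needed. With 33 pairs the logistic test runs slightly above 5% even without confounding, and Fisher runs below it.

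**4. The same check for objective response.** Here n = 33, response is 20%, the true odds ratio for reduction is 1, and the correlation c between baseline and reduction is set directly (assumed).

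| c | Baseline OR 2: apparent OR, rejection | Baseline OR 4: apparent OR, rejection |
|---|---|---|
| 0 | 1.00, 6% | 1.00, 5% |
| 0.3 | 1.22, 8% | 1.39, 13% |
| 0.5 | 1.39, 12% | 1.77, 24% |
| 0.7 | 1.59, 18% | 2.32, 42% |
| −0.5 | 0.73, 14% | 0.57, 27% |

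With baseline included the odds ratio is 1.00-1.01 and rejection is 6-8%. At c = −0.5 the false signal points against suppression.

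**5. Cost of adjusting.** With R² the squared correlation of baseline and reduction, and the odds ratio held at 4.0:

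power = Φ(3.185·√(1−R²) − 1.96).

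This gives 0.856 at R² = 0.10, 0.788 at 0.25 and 0.615 at 0.50. The standard error grows by 1/√(1−R²): about 15% at R² = 0.25 and 41% at 0.50. Under step 2, those two values correspond to rho = 0.5 and rho = 0.

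**6. Events available.** 33 × 0.20 = 6.6 responders, against 33 × 0.34 = 11.2 patients with disease control.

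**The case against.** A reader might infer that the analysis is confounded by construction and that a prognostic baseline would be read as a benefit of suppression. The documents do not support that. They never define reduction as baseline minus Cycle 2 Day 1. A relative measure unrelated to baseline would carry no bias, and the false signal can also point against suppression. Sections 1.3, 2.4 and 9.7.1.6 word the aim as a difference or an association, not as a causal effect. Nor is baseline ignored: question (i) would reveal a prognostic baseline, though it would not adjust for one. The absence of a baseline term is an inference from silence, although the single-predictor power figure supports it.

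It can also be said that the main marker test is Fisher's, that the logistic models are labelled exploratory, and that Fisher stays at about 4-10% over much of the range. The 44% figure requires paired biopsies that share no information (rho = 0) together with a baseline odds ratio of 3. All of this stands. Adjustment is not free either: the more strongly baseline and reduction are correlated, the more precision it costs.

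What survives is that phospho-Rb is a listed secondary objective with its own power table, that neither planned analysis of reduction includes baseline, and that analyzing questions (i) and (ii) separately cannot separate the two explanations.

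**Conclusion.** The point holds as a conditional one. If baseline phospho-Rb is prognostic and correlated with the reduction measure, which is likely for absolute change but is not established by the documents, the unadjusted association could be mistaken for an effect of suppression, in either direction. Under assumed baseline odds ratios of 1.5-3 per SD and rho of 0-0.7, the unadjusted logistic test is falsely positive in about 8-44% of trials and Fisher in about 4-17%, against about 5-7% for the logistic test with baseline included. There is no inflation if either condition fails. The objective response decision rule does not use this analysis and is unaffected, so this is a low-priority improvement.

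**What to change.** In Section 13.4:

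- Keep the Fisher test on disease control as the main marker evaluation.
- Define the quantitative reduction measure: absolute, percent or log-ratio change in H score.
- Add a supporting Firth-penalized logistic model for disease control, with reduction and baseline phospho-Rb H score as covariates, and report it beside the unadjusted result. Disease control is preferred because about 11 events are expected, against about 7 responders; the penalty is there because 11 is still few.
- State that the 89% power applies to the unadjusted model for objective response, and that with baseline included it falls to about 79% at R² = 0.25 and 62% at R² = 0.50, with R² assumed.

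The baseline H score is already planned, so no tissue, visits or patients are added. The cost is analysis work, a less favourable stated power, and appreciably wider intervals for the adjusted estimate when baseline and reduction are strongly correlated.
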